- **Inclusion Criteria:** Women in any stage of labor in participating facility who consent to observation of their delivery and care of their newborn (or consent from the next of kin if the woman is incapacitated and not able to provide consent)
- **Exclusion Criteria:** none

Facility In-charges and Stakeholders

- **Inclusion Criteria:** Facility in-charges at sampled health facilities; stakeholders identified by Jhpiego senior managers as being influential in maternal and newborn health policy decisions in Uganda.
- **Exclusion Criteria:** none

c. Provide **sample size** and a **justification** as to how you arrived at your projected sample size.

The total sample size for this study is 4683 - 2604 health care providers plus 2079 laboring women.

Knowledge and Competency Assessments

For the knowledge and clinical practice assessment, we propose conducting a census of birth attendants working at each facility on the days of training and midline and endline facility data collection. In training interventions, it is routine to test participants before and after the intervention in order to give them feedback to clarify any misunderstandings and improve their performance. We will also do these assessments at baseline and midline facility data collection because we are also interested in collecting data from all providers so that we can do a secondary analysis that will test for a correlation between providers' performance on knowledge assessments and simulator-based performance tests, participation in practice sessions, and directly observed clinical performance. Table 3 presents the maximum number of providers in

the sample facilities, based on data provided by the Ministry of Health; actual enrolled numbers will be lower because not all health care providers on staff will present on the day of data collection. **In addition, we recognize there will be overlap between providers at each time point.** The outcome measure will be a continuous variable measuring ‘correct’ knowledge and competencies across three OSCE exams of BAB or HBB.

Table 3. Number of Providers to be Assessed (c)

Region	Pre and post BAB training (a)	Pre and post HBB Training (a)	Midline Assessment (b) (d)	Endline Assessment (b) (d)	Total Providers in each study group (e)
Districts in Eastern	253	253	253	253	1012
Districts in Western	398	398	398	398	1592
Grand Total	651	651	651	651	2604

Notes

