Provider identifiers will be disposed of 1 year after the project end date. Any paper-based data recordings will be shredded. The electronic files will be deleted.

d. Describe any plans for **destroying data** including if, when and how that will be done. JHU policy states that the PI is the steward of research data and is responsible for all information (recorded on any media) and materials (biological or environmental samples) (see: http://jhuresearch.jhu.edu/Data_Management_Policy.pdf.) This responsibility includes physical custody and/or control of the data, storage and sharing (with data use agreements).

Hard copies of data and electronic recordings of focus group discussions and interviews will be disposed of 1 year after the project end date. Electronic databases without any provider identifiers will remain and will not be destroyed, for possible future additional analyses.

6. Recruitment process:

a. Describe how, and from where, **participants will be recruited**.

All participating providers offering services on the day of birth approved by the facility in charge will be invited to participate in the study. Some providers will be identified by the district authorities and invited to the training on Bleeding After Birth and Helping Babies Breathe. Other providers may learn from those trained providers and be observed by our study.

Peer practice coordinators will be identified by the facility in-charges and district officials from each participating district, and the providers identified will be invited to participate as a PPC. They will receive special training for their PPC role.

Women in labor at the facilities on the days of observation will all be invited to participate. We will approach them in the facility. Data collectors will wait in the maternity ward. They will be approached after they have been admitted for delivery care. Women will be approached at the bedside, as soon as possible, to avoid enrolling women in advanced labor. If they are in the second stage of labor, experiencing a complication, or otherwise in distress, we will seek consent from the person that accompanied them.

Stakeholders will be identified based on the knowledge of Jhpiego/Uganda leadership and in consultation with the Uganda Ministry of Health. They will be contacted at their place of work in person and asked to participate in the study.

b. Explain how your **recruitment materials** will be used.

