No written recruitment materials will be used. Both health care workers and pregnant women will be recruited orally, immediately before being invited to participate. No recruitment script will be used; the oral consent script will be read to inform potential participants about the study.

c. If relevant, address any **privacy concerns** associated with the recruitment process.

We will seek to ensure privacy for providers and pregnant women by obtaining informed consent in a private room or area.

7. Consent process and documentation:

a. If you will obtain informed consent from participants, identify the countries where the research will take place and the languages into which each consent document will be translated. If the language is unwritten, provide information about how you will ensure accurate and informed translation, including possible use of audio recording.

Country	Consent Document (Indicate "All", or specify each document when translations vary)	Languages
Uganda	Oral Consent #1 (Health Care Providers and PPCs)	English
	Oral Consent #2 (Pregnant Women)	English and Kumam, Lusoga, Runyakitara, Rufumbira and Ateso
	Oral Consent #3 (Stakeholders and Facility In-charges)	English
	Oral Consent #4 (Qualitative Interviews with Providers)	English

b. Describe **who will obtain informed consent** from participants, and how, when and where consent will be obtained. If you include children, be sure that consent is obtained from the person who has the legal authority to provide informed consent. In the U.S., that person is usually a biological parent unless a legal proceeding intervenes. Address this issue for

international studies. Note: Children in foster care may not be enrolled unless investigators request their inclusion and explain and follow local requirements.

All data collectors will be trained in depth on how to obtain informed consent during a one-week data collector training workshop using the, “JHSPH Human Subjects Research Ethics Field Training Guide.”

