The research team will obtain permission from the district authorities and the facility in-charge prior to collecting data at facilities. Verbal informed consent will be requested from health care providers including PPCs at each data collection point – baseline, before each training, midline and endline. At baseline, midline and endline, data collectors will seek informed consent in a private setting such as a closed office or meeting room. Before trainings, the informed consent script will be administered in a group setting, when the participants have gathered in the training room. At subsequent data collection points, individual informed consent will be obtained with each participating provider.

For the direct clinical observations, we will request informed consent from pregnant women (or if she is unable to give consent during labor and delivery, her next of kin); this consent will also serve as a parental permission form to observe treatment provided to the newborn. The age of majority is 18 in Uganda, and pregnant women less than 18 years old are considered emancipated minors, able to provide consent for themselves. In addition, women may come in with obstetric complications that render them unconscious or semi-conscious and unable to provide consent. Because these cases are very important in our assessment of quality of care, we propose to ask the next of kin to provide consent for incapacitated pregnant women.

c. If the study will involve **vulnerable populations** (e.g., children, prisoners, cognitively impaired adults, non-English-speakers, etc.) describe efforts to ensure their understanding of the research and the **extra protections** that will be in place to ensure their voluntary participation. Include a description of your assent process for children of appropriate age and maturity; and for adults who lack capacity to provide informed consent.

The consent form will be written in simple language and read aloud in the language commonly used, Luganda, in the study area to ensure that it is understood.

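### Section 6a lets a companion consent for a woman who could consent herself, against Sections 3b and 7b, and Section 7c names a consent language that Section 7a does not list

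*Combined protocol and SAP*

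**What the plan says.** **Who may consent.** The inclusion criterion for observed women in Section 3b admits "Women in any stage of labor in participating facility who consent to observation of their delivery and care of their newborn". Its only alternative is "consent from the next of kin if the woman is incapacitated and not able to provide consent". No exclusion criterion is set. Section 7b asks the pregnant woman, "or if she is unable to give consent during labor and delivery, her next of kin". It then adds women left unconscious or semi-conscious by complications, again naming the next of kin.

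Section 6a invites every woman in labour on observation days and has her approached early. It continues: "If they are in the second stage of labor, experiencing a complication, or otherwise in distress, we will seek consent from the person" who came with her.

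**Language.** For the pregnant women's oral consent, the table in Section 7a lists "English and Kumam, Lusoga, Runyakitara, Rufumbira and Ateso". Section 7c has the form "read aloud in the language commonly used, Luganda, in the study area". Section 7c also promises that all women in labour will understand that taking part is voluntary, and that they can put questions in their own language.

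**What surrounds these rules.** Section 7d asks for a waiver of signed consent. Note (c) to Table 5 in Section 3c gives teams a target number of births and has them stop when it is reached. Table 7 lists the instruments, and none records women approached, refusing, missed or enrolled by proxy.

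**The concern.** Consent is the only condition, beyond being in labour at a study facility, that decides whether a birth is observed. Two different rules for obtaining it are therefore two different definitions of the observed sample, and the primary outcome for postpartum haemorrhage in Section 4b5 comes from these observations.

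The first thing at stake is the protection of the women. A data collector who follows Section 6a to the letter can enrol a conscious woman through a companion, which the inclusion criterion does not allow and which does not secure the voluntariness promised in Section 7c. One who follows Section 7c on language reads out a script in a language that is not on the approved list.

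The second is who ends up observed. Section 6a names only an accompanying person for women who arrive late or in difficulty, and does not say what happens when nobody has come with them. If some teams pass such women over, the observed births tilt towards easier arrivals and nothing in the listed records would show it.

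**Working it through.** The point is textual and no figure in the plan is at stake, so the check applies each rule to the same woman.

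| Woman | Sections 3b and 7b | Section 6a | Result |
|---|---|---|---|
| Able to consent, second stage, with a friend | She is asked | The friend is asked | Conflict on when a proxy applies and on who it is |
| Able to consent, second stage, with next of kin | She is asked | The relative is asked | Conflict on when a proxy applies |
| Unable to consent, with next of kin | Next of kin | The same person | Agreement |
| Unable to consent, brought by someone not kin | Next of kin only, who is not there | The person who brought her | Conflict on who the proxy is |
| Able to consent, second stage, alone | She is asked | Nobody is named | Section 6a silent |
| Unable to consent, alone | Next of kin, who is not there | Nobody is named | No workable route in either |

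The rules agree in one case of six. In three they conflict, and in the two cases of a woman alone Section 6a names nobody.

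**Language.** Section 7a lists English and five local languages for women. Luganda is not one of them. The documents do not say whether any study district needs it.

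**Effect on the observed sample.** Table 5 sets targets of 567 + 756 + 756 = 2,079 births over the three rounds. Because teams observe until the target is met, a missed woman is replaced by another. The number of births does not fall; only their mix can change.

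Let f be the share of eligible births missed, and d the coverage among observed births minus coverage among missed births. The true proportion is (1 − f) × observed + f × missed, so:

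- shift within one group = observed − true = f × d;
- shift in a contrast between arms A and B = f_A × d_A − f_B × d_B, which is zero when the loss is the same in both.

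The documents give neither f nor d. Purely as assumed values, f from 2% to 20% and d from 10 to 30 points give a within-group shift of 0.02 × 10 = 0.2 to 0.20 × 30 = 6.0 points. This shows how the shift scales; it does not estimate it.

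**Could loss differ by arm?** Arms are assigned by district: 12 districts over 3 arms is 12 / 3 = 4 per arm. With so few units, differences in how teams resolve the conflict need not average out. Nothing in the plan shows that teams would differ.

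**The case against.** The best defence is that Section 6a is practical shorthand for Section 7b. Section 7b first covers a woman unable to consent during labour and delivery, then adds unconscious women as a further group, so its first category is wider than unconsciousness. Second stage, complication and distress could be read as examples of that inability, and Section 6a does not say in terms that the woman is bypassed. Women are also approached early, all data collectors share one consent training, and women's questions are answered in their own language.

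Part of this stands. The reading narrows the conflict with Section 7b over when a proxy applies. It does not remove it: Section 6a names clinical states, not inability, and Section 3b requires incapacity. On who the proxy may be, no reading reconciles an accompanying person with next of kin. Answering questions in a local language softens the Luganda mismatch but leaves two different instructions for reading the script.

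Three stronger readings are tempting, and the documents do not support them:

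- **Women who arrive alone are lost from the denominator.** No section excludes them. Section 3b lets such a woman consent for herself, and Section 6a invites all women in labour.
- **Women in advanced labour are ineligible.** Section 6a mentions avoiding their enrolment only as the reason for an early approach, and the same paragraph provides for second-stage women.
- **The plan itself singles out late arrivals as especially important.** The remark in Section 7b about important cases refers to women left unconscious or semi-conscious.

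**Conclusion.** The contradiction over proxy consent holds. Sections 3b and 7b require inability to consent and next of kin; Section 6a requires neither. As written, a woman with capacity can be enrolled on a companion's word, contrary to the inclusion criterion and to the assurance in Section 7c. The language mismatch between Sections 7a and 7c also holds. Neither rests on any numerical assumption.

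The consequence for the data is weaker. Women in second stage or distress who arrive alone are not addressed and may be missed. With a fixed target and no listed log, that could shift case mix unseen. Its size cannot be derived from the documents. A reader might infer that the comparison between arms is biased, but the written procedure is the same in every arm and round, and bias would need the loss, or the difference between missed and observed women, to vary between them. That is possible and not shown. The consent scripts were not available for this check, so whether they settle any of these points is not known.

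The correction is worth making before data collectors are trained, because consent cannot be put right after a birth has been observed.

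**What to change.** 1. Reconcile Sections 3b, 6a and 7b into one rule: a proxy is used only when the woman is unable to consent.
2. Define who may act as proxy in the same words throughout, and say what happens when an incapacitated woman is not accompanied by her next of kin. A bare next-of-kin restriction would drop some of the incapacitated women whom Section 7b wants included.
3. State that a woman with capacity who arrives alone is asked herself, at any stage of labour.
4. In Section 7c, replace Luganda with the languages of Section 7a, or add Luganda to that list if a study district needs it.
5. Add to the observers' records a tally, without identifiers, of eligible, self-consented, proxy-consented, refused and missed births, by arm and round, and report it.

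The cost is a few sentences of protocol text and slightly more recording on observation days. A few births will go unobserved where a companion would have agreed but the woman declines or cannot be asked in time. Because teams work to a target, those births are replaced, possibly with somewhat longer time at a facility.

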JHSPH Institutional Review Board**RESEARCH PLAN**

PI:	[name], Jhpiego		
Co-investigators in Uganda:	[name], Jhpiego Uganda [name], PREFA (Uganda) [name]. [name], Ugandan Ministry of Health [name], Jhpiego Uganda [name], PREFA	Co-Investigators in United States:	[name], Jhpiego [name], Jhpiego [name], Jhpiego [name], Jhpiego [name], AAP

Study Title: Saving Lives at Birth in Uganda: Building and Sustaining Capacity of Frontline Health Workers – A Program Evaluation**IRB No.: 5383****PI Version Number/Date:** Version 2/December 20, 2013

- Aims/objectives/research question/hypotheses:** Describe the primary and secondary aims/objectives of the research, or the project's research questions or hypotheses.

Study Aim:

The study aims are to evaluate the impact of supportive follow-up strategies for a novel twinned training and capacity-sustaining program among frontline health workers (providers) attending facility-based births in remote and district level health facilities in Uganda. The program is designed to improve provider competencies, provider performance and health outcomes among women giving birth and newborns. The goal is to reduce postpartum hemorrhage (PPH) and birth asphyxia -- leading causes of maternal and newborn mortality. Two curricula will be evaluated: Helping Mothers Survive: Bleeding After Birth (HMS: BAB) and of Helping Babies Breathe (HBB).

The objectives are presented in order of an evaluation logic model: Process, Outputs, Outcomes, and Impact.

Objectives of the Evaluation:

Objective 1 (PROCESS): Improve and sustain the frequency of **providers' practice sessions** each week of key PPH and newborn care interventions.

Objective 2 (OUTPUTS): Improve and sustain **provider competencies** during simulation training related to key PPH and newborn care practices, as measured by the percent of providers who pass, and the mean 'correct' score on the knowledge and Objective structured clinical examination (OSCE) assessments of a) HMS: BAB and b) HBB.

Objective 3 (OUTCOMES): Improve and sustain **provider performance** of routine, immediate PPH-prevention and newborn care practices for all mothers/newborns: as measured by the percent of: a) women who received oxytocin or misoprostol within 1 minute of vaginal birth, b) the percent of women among whom the placenta is inspected to standard within 15 minutes, c) the percent of newborns checked for breathing within one minute.

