Objective 4 (OUTCOMES): Improve and sustain **case management** of PPH and newborn resuscitation during observations of care, as measured by a) percent of women with undelivered placenta after 30 minutes who are

treated with oxytocin, and b) percent PPH cases that receive repeated dose of oxytocin or misoprostol, c) percent of newborns not breathing at birth who are breathing or being ventilated with bag & mask at one minute.

Objective 5 (IMPACT): Reduce over time: a) the percent of facility-based deliveries who experience PPH; b) the PPH-related case fatality rate, and c) the perinatal death rate (the fresh stillbirth rate and early newborn mortality rate at 24 hours or prior to discharge)¹.

Prior to presenting the hypotheses, we describe briefly below the three study arms and three time points of data collection. More description is provided in the Study Procedures section. (See Figure 1, page 11)

Table 1. Brief Description of Three Study Arms/Groups

Arm	Short Name	Component 1	Component 2	Component 3
		Training onsite (BAB, HBB) of providers, simulators left at facility	Peer Practice Coordinator (PPC) is trained and expected to hold weekly onsite practice sessions with providers	Mobile messages remind all trained providers to practice scenarios; and PPC has weekly mobile support from district trainer
1	Training-only	Yes	No	No
2	Partial Package	Yes	Yes	No
3	Full Package	Yes	Yes	Yes

Hypotheses

Overall Hypothesis: The partial package intervention (one-time, onsite training of providers, combined with low-dose, high-frequency peer-led practice sessions) and the full-package intervention (adding reminders and mobile support) will lead to significant gains in provider competencies (between immediately post-intervention to midline) and provider performance of key interventions *BAB* and *in HBB*, which are both maintained once the active intervention ceases.

Specific Hypotheses:

In BAB and in HBB related to the primary outcomes (see Section 4b5):

1. Provider competencies and performance will not decline (i.e. will be non-inferior) between midline and endline in the *full* package group.
2. Provider competencies and performance will not decline (i.e. will be non-inferior) between midline and endline in the *partial* package group.
3. At endline, the provider competency level and the performance level of the *partial* package group will be significantly higher than those of the training-only group.

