 - Designated Peer Practice Coordinators (PPC) will log their weekly practice sessions on logs (full and partial arms only).
 - Data on the number of reminders that are sent to providers will be recorded, along with logs of calls between trainers and PPCs (full arm only).
 - Aggregated HMIS data related to PPH, newborn care and mortality data will be collected from routine and supplemental HMIS forms.
- When the five months of the active intervention phase is over, then there will be a midline assessment of providers and facilities: this will again involve a facility assessment, provider knowledge test and OSCEs, observation of provider performance, and qualitative data collection at some facilities. This will take place over 2 or 3 days.
- During the same time period, the research team will contact stakeholders by telephone to schedule interviews with them. Then the interviews will be conducted at the stakeholders' offices or another location, if requested by the stakeholder.
- Following the midline assessment, there will be a 'dormant' phase of no active intervention. This is to determine if competencies and performance is maintained by low-dose high-frequency practice in the absence of donor support. We will return six months later for an endline assessment, which is the same as the midline assessment except there will be no qualitative component.

Table 7. – Description of Data Collection Instruments

Tool #	Title	Content
1	Health Worker Listing	Name and cadre for each health worker at each facility. This will be used to generate a unique ID for each provider
2	Facility Inventory	Information about the tools and equipment available at the facility related to the study intervention, such as the availability of uterotonic drugs and neonatal resuscitators.
3	Direct clinical observation tool	Structured checklist that observers will use to take notes on the care provided to women and neonates, including routine care and treatment for postpartum hemorrhage or neonatal asphyxia.
4	Supplemental maternity register	Note: We will provide this register to facilities, but Jhpiego researchers will not abstract individual records from this document (facility staff will do this). This register collects data about each birth that is relevant to this study, such as whether a woman was diagnosed with postpartum hemorrhage and whether a newborn received bag & mask resuscitation.

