16	Semi-structured interview guide: Health care providers	Health care providers will be asked about their experiences with the program and their ideas for how to improve care for postpartum hemorrhage and neonatal asphyxia.
17	Semi-structured interview guide: Stakeholders	Stakeholder will be asked about their opinions about how to strengthen and sustain this program and other efforts to improve care for postpartum hemorrhage and neonatal asphyxia in Uganda.

3) *Number of study contacts* or visits required of participants.

Please see table 2 on page 5 for details. Briefly, women in labor, key stakeholders and facility in-charges will each have a maximum of only one study contact. Providers could have up to 12 study contacts, if they were selected for all types of data collection, but this will be rare. Similarly, peer practice coordinators could have up to 12 study contacts plus regular telephone contact with a member of the research team.

4) **Expected duration of the study.**

After JHSPH IRB and Ugandan IRB are obtained, the study will take 18 months.

5) A brief **data analysis plan** and description of the **nature of the variables** to be derived.

Primary Outcome:

- For the postpartum hemorrhage component, the primary outcome will be the proportion of women who received **oxytocin** (at correct dosage) within one minute of a vaginal birth, before delivery of the placenta. Data for this outcome will be obtained from the direct clinical observations.
- For the neonatal asphyxia component, the primary outcome will be the proportion of babies not breathing at birth who are breathing or being ventilated by one minute.

Secondary Outcomes:

- Change in providers' knowledge and competence related to postpartum hemorrhage and neonatal resuscitation, as assessed by knowledge tests and observed performance with a simulator.
- Trends in PPH and neonatal asphyxia/mortality rates, by abstracting *aggregated* monthly service statistics from each facility.
- Identification of structural, environmental and behavior factors that are associated with routine, frequent practice with the simulator.

Data will be entered using [name]/Foxpro/SPSS/CsPro and analyzed using Stata 12.

Quantitative data analysis

Specific Hypotheses:

In BAB and in HBB related to the primary outcomes (see Section 4b5):

1. Provider competencies and performance will not decline (i.e. will be non-inferior) between midline and endline in the *full* package group.

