If sub-standard (actual) care is observed and deemed dangerous by observers	There is a possibility that the actual care provided to the woman in labor or delivery or the newborn is sub-standard and dangerous for the mother or babies' survival (related to reality of the situation, not the observation).	
Where available, a senior provider (physician or midwife) will be notified that on the day of assessment, the senior provider must be present in the facility or immediately reachable and available in order to be called in for assistance in cases where patients' health status or safety is compromised and is not being appropriately managed by the observed provider. This requirement will be outlined in a letter from the MoH and in country PI that will be sent to the director of selected facilities that will inform them that their facility has been selected for assessment in the survey, describing the assessment and activities in the facility and requesting their cooperation. It will also outline the requirement that on the date of assessment where available, a senior provider must be made aware that they may be called in to intervene and should be onsite or immediately available. If a second provider is not available, the study observer who is a senior clinician can choose to intervene.
 
This condition may intensify the potential Hawthorne effect of being observed - where the observed provider changes their behavior in response to being observed. Knowledge that another [senior] staff member could be called to assist in case of a complication may intensify this effect, such that quality of care observed may be better than routinely provided, but this potential effect is acceptable given the necessity to ensure optimal patient care and safety.

b. Describe the **anticipated frequency and severity of the harms** associated with the risks identified in 8.a., above; for example, if you are performing “x” test/assessment, or dispensing “y” drug, how often do you expect an “anticipated” adverse reaction to occur in a study participant, and how severe do you expect that reaction to be?

We expect any harm associated with the above risks to be rare. Since we are providing no treatment as part of this study, adverse reactions would not be expected.

c. Describe steps to be taken to **minimize those risks**.

See above table, column 3.

d. Describe the **research burden** for participants, including time, inconvenience, out-of-pocket costs, etc.

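### No rule keeps care triggered by the study observer from counting as provider performance at observed births

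*Combined protocol and SAP*

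**What the plan says.** The row of the Section 8a risk table on dangerous sub-standard care asks that a senior provider, where there is one, be on hand on assessment days, to be called "in cases where patients' health status or safety is compromised and is not being appropriately managed by the observed provider". It continues: "If a second provider is not available, the study observer who is a senior clinician can choose to intervene". Section 9a lists the extra support as a possible benefit to observed women. The same row names one consequence for measurement, the Hawthorne effect, "such that quality of care observed may be better than routinely provided, but this potential effect is acceptable".

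The outcomes are worded by what the woman or newborn received:

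- Section 4b5, HBB: "the primary outcome will be the proportion of babies not breathing at birth who are breathing or being ventilated by one minute".
- Section 4b5, PPH: oxytocin at the right dose within a minute of birth. The section adds: "Data for this outcome will be obtained from the direct clinical observations".
- Section 1, Objective 3, labelled provider performance: "women who received oxytocin or misoprostol within 1 minute of vaginal birth".
- Section 1, Objective 4, labelled case management: "percent PPH cases that receive repeated dose of oxytocin or misoprostol", together with oxytocin for a placenta still undelivered at 30 minutes and the newborn measure above.

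Table 7 describes the observation instrument, Tool 3, as a "Structured checklist that observers will use to take notes on the care provided to women and neonates". Section 4b5 has no rule to flag, rescore or separately analyse a birth at which the observer called for help or acted.

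**The concern.** The safety rule operates only when the observed provider is failing. If the help it brings is scored as care received, a failure becomes a success in a measure that is meant to describe the facility's own providers. That is not the Hawthorne effect. There, the provider behaves better because someone is watching. Here, another person's care, present only because the study is present, enters the numerator. Accepting the first effect does not settle the second, and the second can be recorded and removed.

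Three uses of the data are at stake: the endline comparisons between arms (Hypotheses 3 and 4), the claim that performance is maintained from midline to endline (Hypotheses 1 and 2), and the secondary analysis in Section 3c that relates test scores to observed performance.

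**Working it through.** **The plan's own figures.** Note (b) to Table 5 gives 50% against 65%, 80% power and ICC 0.01. It states neither alpha nor cluster size; I assume two-sided 0.05 and the 54 facilities of note (a), so m = 189/54 = 3.5.

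- The two-proportion formula gives 170 per arm, or 183 with continuity correction.
- Design effect = 1 + (3.5 − 1) × 0.01 = 1.025, and 183 × 1.025 = 188, against the stated 189.
- Note (a): 70% at both times, margin 0.10, alpha 0.025 gives 330. With ICC 0.005 this is about 339, and rounding up to 7 births in each of 54 facilities gives 378.

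Both figures reproduce.

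**Effect on an arm difference.** Let f0 and f1 be the true failure proportions in training-only and intervention, and r0 and r1 the shares of failures rescued and scored as success. The reported difference is f0(1 − r0) − f1(1 − r1). With equal r it is (f0 − f1)(1 − r). The documents give no value for r, so the range below is an assumption (189 births per arm, design effect 1.025, f0 = 0.50, f1 = 0.35):

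| r, both arms | Reported difference | Power |
|---|---|---|
| 0 | 15.0 points | 83% |
| 5% | 14.25 | 80% |
| 10% | 13.5 | 76% |
| 20% | 12.0 | 68% |
| 30% | 10.5 | 60% |

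With unequal shares:

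- 10% in training-only and 5% in intervention: 0.50 × 0.90 − 0.35 × 0.95 = 11.75 points, power 64%.
- 5% and 10%: 0.50 × 0.95 − 0.35 × 0.90 = 16.0 points, power 89%. The difference grows.

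At these rates it grows whenever r1 exceeds r0 × 0.50/0.35 = 1.43 r0.

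**Effect on non-inferiority.** Take a true fall from 70% to 60%, exactly the 0.10 margin, with 378 births per time point, ICC 0.005 and equal r at both times. The reported fall is 10 × (1 − r) points. The chance of claiming non-inferiority rises from 2.5% (r = 0) to 3.5% (5%), 4.8% (10%) and 8.8% (20%).

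These two calculations use oxytocin inputs because only that outcome is sized. They show the mechanism, not an expected loss for oxytocin.

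**Leverage of one rescued PPH case.** Section 2 cites a global PPH incidence of 10.8%, with a regional range of 7.2% to 25.7%. Table 5 gives 189 births per arm and round, except 378 in the full arm at midline and endline.

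- 189 births: 189 × 0.072 = 14, × 0.108 = 20, × 0.257 = 49 cases. One case is 1/14 = 7 points down to 1/49 = 2 points.
- 378 births: 378 × 0.072 = 27, × 0.108 = 41, × 0.257 = 97 cases. One case is 1/27 = 4 points down to 1/97 = 1 point.

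**Exposure by outcome.** Objective 4(a)-(b) concerns complications that unfold over many minutes, so help has time to arrive and be scored. The HBB primary closes at one minute: the observer must see the problem, judge it dangerous and get help within that time. Oxytocin within one minute has the same short window, and its omission is less likely to be judged a danger by then. The documents give no frequency for non-breathing newborns or undelivered placentas, so those denominators cannot be sized.

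**The case against.** The strongest reply is that the documents are silent. They do not say that rescued care is counted. Tool 3 is known only from a short summary, and the full checklist may contain an item on who acted. That stands: the supportable statement is that no written rule prevents the counting, not that the plan does it.

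Second, the most exposed measures carry the least weight. Objective 4(a)-(b) is neither a primary nor a listed secondary outcome in Section 4b5, and is not among the dependent variables for Hypotheses 3 and 4. Table 2 also names facility registers as a source for Objective 4, and births outside observation days are untouched. Both primaries close at one minute. The non-inferiority analysis in Section 4b5 is written for knowledge and competence scores, which help at a birth cannot change. All this limits the harm without removing it: Hypotheses 1 and 2 also cover performance, and Section 3c sizes a non-inferiority comparison on observed oxytocin.

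Third, a reader might infer that the bias always runs toward no difference. It need not. Equal rescue shares are an assumption, and blinding of observers to arm is not described.

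Fourth, a reader might infer that these events go unmonitored. Section 13 sets a reporting chain for adverse events at the time of data collection. It does not, however, count observer-triggered help by arm.

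**Conclusion.** The gap is real and narrow. A rule triggered by provider failure brings in outside care, the outcomes do not attribute care, and nothing written separates the two. The bias is potentially material for Objective 4(a)-(b), where one case can move a percentage by 2 to 7 points (1 to 4 in the full arm at midline and endline). These figures assume that the cited PPH incidences apply to the study facilities. It is smaller for the HBB primary and slight for the oxytocin primary.

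The total size is unknown because it depends on r. Up to r = 5% the illustrative loss of power is about 3 points; from 10% to 30% it would matter. Shrinkage is assured only if the rescue share is equal across arms or higher in training-only. A midline-to-endline decline can be masked. The documents do not support the stronger conclusion that the primary comparisons are invalid. This is a cheap improvement, worth making before data collection because who acted cannot be reconstructed afterwards.

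**What to change.** The safety rule in Section 8a stays unchanged.

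1. **Tool 3.** Add a timed item: whether the observer called for help or intervened, at what time, who acted, and which steps they performed.
2. **Section 4b5.** For the HBB primary and Objectives 3 and 4, score a step supplied by the observer, or by the person the observer called, as not performed by the facility provider. For the HBB primary, a baby who meets the one-minute criterion only through such help is scored as not achieved. Steps the provider performs personally, or with help the provider seeks unprompted, still count.
3. **Reporting.** Give the number of observer-triggered interventions by arm and round.
4. **Sensitivity analyses.** Score care as received, and separately score every step after the observer's call as not performed. The second is too harsh as the main rule, because it would fail a provider who completes a step personally after a call made for another reason.

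The cost is one checklist item and a short scoring rule. Reported performance percentages may fall slightly, and attribution relies on observers who may know the arm; the two sensitivity analyses bracket that reliance.
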